## 9.5 Reporting safety information to the IRB/EC

The Investigator is responsible for following all local regulations for the reporting of safety information, including the reporting of SAEs to the IRB/ EC.

The Investigator must promptly report to his or her IRB/EC all unanticipated problems involving risks to subjects. This includes death from any cause and all serious adverse events reasonably or possibly associated with the use of study drug. It is recommended that all SAEs occurring at a site, regardless of causality, be reported to the site's IRB/EC in accordance with the IRB/EC's requirements.

Lasmiditan has been filed under an Investigational New Drug (IND) application with the US FDA. An SAE may require safety reports to be filed to regulatory agencies if the SAE is related to the study drug and is unexpected based upon the current Investigator's Brochure. In this case, the Investigator will receive a copy of the safety report as submitted to the regulatory agencies. The Investigator is responsible for submitting the safety report (initial and follow-up) or other safety information (e.g., revised Investigator's Brochure) to the IRB/EC in accordance with the IRB/EC's requirements and keep a copy in their files.

## 9.6 Pregnancies

To ensure subject safety, each pregnancy in a subject on study drug must be reported to the medical monitor within 24 hours of learning of its occurrence. Subjects who become pregnant will be withdrawn from the study. The pregnancy should be followed up to determine outcome, including spontaneous or voluntary termination, details of the birth, and the presence or absence of any birth defects, congenital abnormalities, or maternal and/or newborn complications.

Pregnancy should be recorded on a subject's source documents and a Pregnancy Notification and Outcome Form and reported by the Investigator to Quintiles Pharmacovigilance using the same procedure for reporting SAEs in [Section 9.3](#). A pregnancy, by itself, is not a SAE. Pregnancy follow-up should also be recorded and should include an assessment of the possible relationship to the study drug of any pregnancy outcome. Any pregnancy-related SAE (e.g. spontaneous abortion) or any other SAE experienced during pregnancy must be recorded on a separate SAE Report Form and reported per SAE reporting procedures in [Section 9.3](#).

## 10. STATISTICS

Prior to locking and unblinding the database, a detailed statistical analysis plan will be developed before any receipt of study data and decisions will be made regarding the integrity of subject data for inclusion in the statistical analysis. The efficacy analyses and baseline characteristics will be based on the Intent-to-Treat (ITT) and mITT population. The primary analysis will be tested in the mITT population. All safety analyses will be based on the Safety Population. The Per Protocol Population will be used to support the ITT analyses.

All tests of treatment effects will be conducted at a one-sided alpha level of 0.025.

The primary objective of the study is to evaluate the efficacy of lasmiditan versus placebo at 2 hours on migraine headache pain and the MBS as identified by the individual subject based on the first dose.

Summary analysis of the efficacy and safety of the use of a second dose of lasmiditan versus placebo for either rescue or recurrence will be performed only in the subjects that actually took a second dose of study drug within 24 hours of the first dose. Analysis will be performed on the subset of subjects that dosed for rescue and on the subset that dosed for recurrence of migraine.

Data from all investigative sites will be pooled for all planned analyses. Analysis of individual site findings will be considered if necessary. For those measures that are analyzed using change from baseline scores, observed scores may also be presented descriptively.

Any changes in the data analysis methods described in the protocol will require an amendment only if it changes a principal feature of the protocol. Any other changes to the data analysis methods described in the protocol and the justification for making the change will be described in the statistical analysis plan as well as the clinical study report. Additional exploratory analyses will be conducted as deemed appropriate. All data listings, summaries and analyses will be performed by Quintiles.

### 10.1 Sample Size

This Phase 3 study is designed to demonstrate that lasmiditan is effective in the treatment of acute migraine in adult patients with and without aura. The sample size was estimated based on the 2 hour headache pain free and associated symptoms (nausea, phonophobia, and photophobia) free response rates observed in the Phase 2 study [COL MIG-202](#).

Dose	Pain free	Nausea free	Phonophobia free	Photophobia free
Placebo	7.4%	59.3%	51.9%	34.6%
50 mg	13.9%	68.4%	58.2%	53.2%
100 mg	13.6%	74.1%	75.3%	67.9%
200 mg	18.8%	63.8%	59.4%	58.0%

For the primary endpoint of the proportion of patients pain free at 2 hours a sample size of 570 evaluable subjects per arm provides power of >90% for the 50 mg dose, the 100 mg dose and the 200 mg dose.

In order to estimate sample size for the key secondary endpoint of proportion of patients MBS free at 2 hours, simulation was performed in SAS on the conditional probability of being free from any one symptom defined as MBS under 4 different scenarios. For each symptom or combination of symptoms, the likelihood of an individual symptom being the MBS was estimated. In the most conservative scenario (scenario 1) it was assumed that nausea would always be declared the MBS if it was present, regardless of the presence of other symptoms (phonophobia or photophobia). The other 3 scenarios assumed lower likelihoods of nausea to be considered the MBS and allowed for the other symptoms (either phonophobia or photophobia) to be considered the MBS at a higher rate. This resulted in power estimates of > 95% for MBS at a sample size of 570 for the lasmiditan 50 mg dose and >99% for MBS at sample sizes of 450 to 570 per arm for the 100 mg dose across all 4 scenarios. For the 200 mg dose, an average power of 71% was estimated across five seeds under the most conservative scenario 1. In contrast, the 3 scenarios that did not declare nausea to be the default MBS if it was present estimated a greater average power of 82.6% to 91%.

Group	Scenario	Variable	Seed				
			55405	74951	82002	82377	90075
Placebo vs D50	1	Power (MBS)	96.90%	95.90%	96.10%	95.60%	96.80%
		Sample Size	570	570	570	570	570
	2	Power	93.70%	94.30%	94.80%	93.90%	93.90%
		Sample Size	450	450	450	450	450
	3	Power	90.40%	90.40%	90.10%	91.00%	91.40%
		Sample Size	575	575	575	575	575
	4	Power	93.70%	94.30%	94.80%	93.90%	93.90%
		Sample Size	450	450	450	450	450
Placebo vs D100	1	Power (MBS)	>99.99%	>99.99%	>99.99%	>99.99%	>99.99%
		Sample Size	570	570	570	570	570
	2	Power	99.90%	>99.99%	>99.99%	>99.99%	>99.99%
		Sample Size	450	450	450	450	450
	3	Power	>99.99%	>99.99%	>99.99%	>99.99%	>99.99%
		Sample Size	575	575	575	575	575
	4	Power	99.90%	>99.99%	>99.99%	>99.99%	>99.99%
		Sample Size	450	450	450	450	450
Placebo vs D200	1	Power	70.87%	70.87%	72.97%	71.17%	68.47%
		Sample Size	570	570	570	570	570
	2	Power	84.40%	85.00%	85.80%	85.90%	85.80%
		Sample Size	450	450	450	450	450
	3	Power	83.50%	83.20%	81.30%	83.40%	81.80%
		Sample Size	575	575	575	575	575
	4	Power	90.20%	90.50%	92.50%	91.40%	90.40%
		Sample Size	450	450	450	450	450

 Mean rate is the freedom from MBS at 2 hours post dose.  
P=placebo, L = lasmiditan

It is expected for a one-sided, two-sample comparison of proportions at the 2.5% level of significance, a sample size of 570 subjects per treatment arm (as defined by the first dose) provides >90% power to detect a difference in headache pain free response rates for assumed true rates of 7.4% and 18.8% (placebo and 200 mg), 7.4% and 13.6% (placebo and 100 mg) and 7.4% and 13.9% (placebo and 50 mg) >90 % power for MBS for both the 50 mg dose arm

and the 100 mg dose arm and very near or higher than 80% power for MBS in the 200 mg dose arm.

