## 10.2 Randomization

This is a multicenter, randomized, double-blind, placebo controlled parallel group study. Subjects will be centrally randomized to one of 7 treatment sequences to receive lasmiditan 50 mg, lasmiditan 100 mg (L100 mg) or lasmiditan 200 mg (L200 mg) or placebo (P) for the first dose (in a 1:1:1:1 ratio) and the second dose for rescue or recurrence of migraine (if needed). Subjects will be stratified (yes or no) for use of concomitant medications that reduce the frequency of migraine episodes. Study drug will be randomized and dispensed at **Visit 1** as follows:

First dose for treatment of migraine	Second dose for rescue or recurrence of migraine (if needed)
L50 mg	L 50 mg
	L 50 mg
	placebo
L100 mg	L100 mg
	L100 mg
	placebo
L200 mg	L200 mg
	L200 mg
	placebo
placebo	placebo

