#### **10.5.3 Multiplicity Adjustment for Hypothesis Testing**

The gatekeeping procedure will be implemented to prevent Type I error inflation for multiple comparisons among the primary and secondary analyses. The treatment effect between lasmiditan 200 mg and placebo will be tested first for the primary endpoint of the proportion of subjects who are headache pain free and the key secondary endpoint of the proportion of subjects who are MBS free at 2 hours in the mITT population.

If the primary analysis is statistically significant (one-sided,  $p < 0.025$ ), additional confirmatory hypotheses will be tested in the mITT population in the following sequential order:

1. Proportion of subjects who are headache pain free at 2 hours in the lasmiditan 100 mg and placebo group.
2. Proportion of subjects who are MBS free at 2 hours in the lasmiditan 100 mg and placebo group.
3. Proportion of subjects who are headache pain free at 2 hours in the lasmiditan 50 mg and placebo group.
4. Proportion of subjects who are MBS free at 2 hours in the lasmiditan 50 mg and placebo group.

All of the above analyses will be completed using one-sided tests at the  $\alpha=0.025$  level of significance. If one of the analyses is not statistically significant, then all subsequent analyses will be exploratory rather than confirmatory.

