	2	Power	99.90%	>99.99%	>99.99%	>99.99%	>99.99%
		Sample Size	450	450	450	450	450
	3	Power	>99.99%	>99.99%	>99.99%	>99.99%	>99.99%
		Sample Size	575	575	575	575	575
	4	Power	99.90%	>99.99%	>99.99%	>99.99%	>99.99%
		Sample Size	450	450	450	450	450
Placebo vs D200	1	Power	70.87%	70.87%	72.97%	71.17%	68.47%
		Sample Size	570	570	570	570	570
	2	Power	84.40%	85.00%	85.80%	85.90%	85.80%
		Sample Size	450	450	450	450	450
	3	Power	83.50%	83.20%	81.30%	83.40%	81.80%
		Sample Size	575	575	575	575	575
	4	Power	90.20%	90.50%	92.50%	91.40%	90.40%
		Sample Size	450	450	450	450	450

It is expected for a one-sided, two-sample comparison of proportions at the 2.5% level of significance, a sample size of 570 subjects per treatment group (as defined by the first dose) provides >90% power to detect a difference in headache pain-free response rates for assumed true rates of 7.4% and 18.8% (placebo and 200 mg), 7.4% and 13.6% (placebo and 100 mg), and 7.4% and 13.9% (placebo and 50 mg) >90 % power for MBS for both the 50 mg dose arm and the 100 mg dose arm and very near or higher than 80% power for MBS in the 200 mg dose arm.

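### The >90% power stated for 100 mg and 50 mg is single-comparison power; under the test sequence it is capped by 200 mg MBS-free, at about 71% in scenario 1

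*Protocol*

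**What the plan says.** Protocol 10.1 (repeated in the synopsis and SAP 2.2) states that 570 evaluable subjects per arm "provides power of >90% for the 50 mg dose, the 100 mg dose and the 200 mg dose" for pain freedom at 2 hours. The basis is a "one-sided, two-sample comparison of proportions at the 2.5% level of significance". The closing paragraph adds >90% power for MBS-free at 50 mg and 100 mg.

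For 200 mg MBS-free the same section is less favourable: "For the 200 mg dose, an average power of 71% was estimated across five seeds under the most conservative scenario 1". The other three scenarios average 82.6% to 91%. The closing paragraph sums this up as "very near or higher than 80% power for MBS in the 200 mg dose arm".

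Protocol 10.5.3 puts both 200 mg endpoints before any lower dose, then 100 mg pain-free, 100 mg MBS, 50 mg pain-free and 50 mg MBS. On failure of a step: "If one of the analyses is not statistically significant, then all subsequent analyses will be exploratory rather than confirmatory". The synopsis requires both 200 mg analyses to succeed before going on. SAP 11.1 makes 200 mg MBS-free the first step after the primary test, with the same stopping rule. The documents label the 200 mg MBS test differently, but in both it comes before every 100 mg and 50 mg test.

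**The concern.** Neither sample-size section mentions the sequence or gives a power that allows for it. The primary objective covers all three doses, so the useful figure for 100 mg and 50 mg is the chance of a confirmatory result. That chance depends on 200 mg MBS-free, the comparison with the lowest simulated power in scenarios 1 to 4. If it fails, all four lower-dose tests become exploratory however strong they are. In scenario 1 that happens about 29% of the time (1 - 0.709), while someone who takes the >90% as the chance of a confirmatory finding would put the risk per test below 10%.

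**Working it through.** **Inputs.** One-sided alpha 0.025; 570 per arm; 1:1:1:1 allocation with one placebo arm; pain-free rates 7.4% (placebo), 18.8% (200 mg), 13.6% (100 mg) and 13.9% (50 mg); MBS powers from the seed table. All are in protocol 10.1 and 10.2.

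**1. The plan's own figure.** Two-sample z power = Φ{[Δ - 1.96·√(2p̄(1-p̄)/n)] / √([p0(1-p0)+p1(1-p1)]/n)}.
- 100 mg: (0.062 - 1.96×0.01816)/0.01807 = 1.46, power 92.8%.
- 50 mg: (0.065 - 1.96×0.01827)/0.01817 = 1.61, power 94.6%.
- 200 mg: 99.99%.

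A Wald test on the log odds ratio, nearer to the planned logistic analysis, gives 92.0%, 93.9% and 99.98%. The stated >90% is right for each comparison alone.

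**2. Power of 200 mg MBS-free.** Mean of the five printed seeds. Scenario 1, for example: (70.87+70.87+72.97+71.17+68.47)/5 = 70.87%. The table was run at different sample sizes, so I also rescaled to 570: Φ{(1.96+Φ⁻¹(power))·√(570/n) - 1.96}.

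| Scenario | Printed n | Printed mean | At n=570 |
|---|---|---|---|
| 1 | 570 | 70.9% | 70.9% |
| 2 | 450 | 85.4% | 92.4% |
| 3 | 575 | 82.6% | 82.3% |
| 4 | 450 | 91.0% | 96.0% |

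**3. Limits that need no correlation.** The chance of passing a run of tests cannot exceed the power of any one of them. At n=570 every 100 mg and 50 mg test is therefore capped at 70.9% in scenario 1 and 82.3% in scenario 3. The lower limit is the sum of the powers minus (number of tests - 1). For 100 mg pain-free in scenario 1 it is 0.9999 + 0.7087 + 0.9281 - 2 = 63.7%. So that test lies between about 64% and 71% whatever the correlation.

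**4. Cumulative power in the SAP 11.1 order.** With full independence, scenario 1 gives 0.9999 × 0.7087 × 0.9281 = 65.8% for 100 mg pain-free. For a more realistic figure I treated the six test statistics as multivariate normal: correlation 0.5 between doses (equal arms sharing placebo) and an assumed pain/MBS correlation of 0 to 0.8, which the documents do not give. Ranges below cover that assumption and both the z and Wald pain-free powers, with MBS powers at n=570.

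| Scenario | 100 mg pain-free | 50 mg pain-free | 50 mg MBS |
|---|---|---|---|
| 1 | 65-68% | 62-66% | 61-66% |
| 3 | 76-78% | 72-76% | 68-73% |
| 2 (rescaled) | 85-87% | 81-84% | 80-84% |
| 4 (rescaled) | 88-90% | 84-87% | 83-86% |

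The 100 mg MBS test, at >99% power, costs almost nothing. With scenario 4's printed n=450 MBS powers, 100 mg pain-free is 84-86%.

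**5. The closing summary.** Scenarios 2 to 4 are above 80%; scenario 1 is 70.9%, with seeds from 68.47% to 72.97%, none near 80%.

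**The case against.** The strongest reply is that nothing has been miscalculated or hidden. The >90% figures reproduce, and the closing paragraph describes them as two-sample comparisons at stated rates. The 71% appears in prose in the same section, every seed is tabulated, and the sequence is in the same chapter. Reporting power comparison by comparison is common, and a careful reader has what is needed to see the cap.

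Most of that stands. A reader might infer an arithmetic error, or that the weak step was concealed; the documents support neither. Nor is type I error affected: the fixed sequence controls it. It would also be too strong to call 62% to 90% the true power for the lower doses. The lower end comes from the most conservative scenario, the upper end needs rescaling from 450 to 570 per arm, and the pain/MBS correlation is assumed.

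What the reply leaves unanswered is that the 71% is reported only as a 200 mg figure, never as a limit on the other two doses. The closing summary then drops it.

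**Conclusion.** The point holds as a gap in what is reported. The >90% for 100 mg and 50 mg is single-comparison power. The probability of a confirmatory result for either dose is at most about 71% in scenario 1 and about 82% in scenario 3. These limits rest only on the plan's simulated powers and its test order (scenario 3 rescaled trivially from 575 to 570).

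The shortfall in scenarios 2 and 4 is less certain. After rescaling to 570, the correlation-free cap on 100 mg pain-free is 92.4% in scenario 2 (200 mg MBS) and 92.8% in scenario 4 (the 100 mg test itself), so caps alone do not rule out 90%. The modelled values of 85-87% and 88-90% depend on the assumed correlation.

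Separately, the closing phrase on 200 mg MBS power contradicts the plan's own scenario 1 result. A reader might infer that the trial is too small or the order wrong; these figures do not settle that, since the plan sets no target for power through the sequence.

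**What to change.** In the protocol synopsis, protocol 10.1 and SAP 2.2:
- Label the existing figures as single-comparison power.
- Add the power to pass each step of the sequence at 570 per arm, by scenario, with the correlation assumption and its range stated. At minimum, state the correlation-free upper limit.
- Replace the closing phrase on 200 mg MBS power with the actual range, starting at 71%, and give the sample size behind each figure.

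Re-running the existing simulation may not be enough: the documents describe it as a simulation of MBS freedom only, and nothing shows that pain freedom was generated jointly with it. A simple joint normal calculation like the one above suffices. The cost is a short calculation and a text edit, and the stated figures become less favourable. Sample size, alpha and test order do not change.

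### The sample-size summary overstates power for the 200 mg MBS test (about 71% in scenario 1 at 570 per arm), and the plan gives no power for the fixed sequence that this test controls

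*Protocol*

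**What the plan says.** Protocol 10.1, repeated in SAP 2.2, sizes the trial at 570 evaluable subjects per arm. It claims more than 90% power for pain-free at each dose, more than 90% for MBS at 50 mg and 100 mg, and "very near or higher than 80% power for MBS in the 200 mg dose arm".

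Earlier in the same section the text is more detailed. For 50 mg: "This resulted in power estimates of > 95% for MBS at a sample size of 570 for the lasmiditan 50 mg dose". For 200 mg: "For the 200 mg dose, an average power of 71% was estimated across five seeds under the most conservative scenario 1", with 82.6% to 91% in the other three scenarios. The table of simulated MBS power uses different sample sizes by scenario: 570 (scenario 1), 450 (scenarios 2 and 4) and 575 (scenario 3).

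On testing, Protocol 10 states "All tests of treatment effects will be conducted at a one-sided alpha level of 0.025". The protocol synopsis requires both 200 mg tests to succeed before any lower dose is tested. SAP 11.1 gives the full order: 200 mg pain-free, 200 mg MBS, 100 mg pain-free, 100 mg MBS, 50 mg pain-free, 50 mg MBS. Protocol 10.5.3 adds: "If one of the analyses is not statistically significant, then all subsequent analyses will be exploratory rather than confirmatory".

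Both documents attribute the input rates to the same Phase 2 study, but the placebo photophobia-free rate is 34.6% in Protocol 10.1 and 36.4% in SAP 2.2.

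**The concern.** The summary sentence carries no scenario qualifier, yet the section's own most conservative scenario, at the design sample size, falls about 9 points short of 80%. A reader who takes the power from the conclusion gets the wrong lower end.

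This test has the lowest power of the six, and four confirmatory hypotheses sit behind it. If 200 mg MBS misses, every 100 mg and 50 mg result becomes exploratory, however strong. The powers quoted for those doses assume that each test is carried out on its own, and neither document says how likely the trial is to reach them. Someone who reads the figures above 90% as the chance of a confirmatory claim at 100 mg or 50 mg would be too optimistic.

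**Working it through.** **Inputs.** One-sided alpha 0.025 (z = 1.960); 570 per arm, equal allocation on the first dose; pain-free rates 7.4% (placebo), 18.8% (200 mg), 13.6% (100 mg), 13.9% (50 mg); five-seed MBS powers from the table. All are in Protocol 10 to 10.2.

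**Step 1: pain-free power, single test.** Power = Φ[(d − z·SE0)/SE1], with SE0 from the pooled rate and SE1 from the separate rates.

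- 200 mg: d = 0.114, SE0 = 0.01999, SE1 = 0.01970; Φ(3.80) = 99.99%.
- 100 mg: d = 0.062, SE0 = 0.01816, SE1 = 0.01807; Φ(1.46) = 92.8%.
- 50 mg: d = 0.065, SE0 = 0.01827, SE1 = 0.01817; Φ(1.61) = 94.6%.

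Unpooled variance, a continuity correction and a Wald test on the log odds ratio give 91.4-92.9% (100 mg) and 93.4-94.7% (50 mg). The plan's claim of more than 90% reproduces.

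**Step 2: MBS power as printed, and at a common 570.** The MBS-free rates and scenario probabilities behind the simulation are not given, so MBS power cannot be recomputed from rates. I averaged the five seeds and rescaled: λ = Φ⁻¹(power) + 1.960, then power at 570 = Φ(λ·√(570/n) − 1.960).

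| Dose, scenario | n run | Seed range | Mean | At 570 |
|---|---|---|---|---|
| 200 mg, 1 | 570 | 68.47-72.97% | 70.87% | 70.9% |
| 200 mg, 2 | 450 | 84.4-85.9% | 85.38% | 92.4% |
| 200 mg, 3 | 575 | 81.3-83.5% | 82.64% | 82.3% |
| 200 mg, 4 | 450 | 90.2-92.5% | 91.00% | 96.0% |
| 50 mg, 1 | 570 | 95.6-96.9% | 96.26% | 96.3% |
| 50 mg, 2 | 450 | 93.7-94.8% | 94.12% | 97.8% |
| 50 mg, 3 | 575 | 90.1-91.4% | 90.66% | 90.4% |
| 50 mg, 4 | 450 | 93.7-94.8% | 94.12% | 97.8% |

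Example (200 mg, scenario 2): λ = 3.013; 3.013 × √(570/450) = 3.391; Φ(3.391 − 1.960) = 92.4%.

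The text's 71%, 82.6% and 91% for 200 mg reproduce. In scenario 1 even the best seed is 7 points below 80%. For 50 mg, more than 95% is true of the one run at 570 but not of scenario 3, at a slightly larger n. All 100 mg entries are 99.9% or higher.

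**Step 3: ceiling from the sequence.** A test is confirmatory only if all earlier tests succeed, so P(reach and win) ≤ the smallest single-test power up to that step. This needs no correlation. After 200 mg MBS the ceiling is 70.9% in scenario 1 and 82.3% in scenario 3 (82.6% as printed at 575).

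**Step 4: cumulative power.** I simulated the six test statistics as multivariate normal (1,000,000 draws) with the step 1 powers and the step 2 powers at 570, and 99.99% for 100 mg MBS. The correlation between doses is 0.5, from the shared placebo arm and equal allocation. The pain/MBS correlation is not in the documents; I assumed 0 to 0.5.

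| Step | Scen. 1 | Scen. 2 | Scen. 3 | Scen. 4 |
|---|---|---|---|---|
| 200 mg MBS | 71% | 92% | 82% | 96% |
| 100 mg pain-free | 66-67% | 86% | 76-77% | 89-90% |
| 100 mg MBS | 66-67% | 86% | 76-77% | 89-90% |
| 50 mg pain-free | 63-65% | 82-83% | 73-75% | 86% |
| 50 mg MBS | 62-64% | 81-82% | 69-71% | 84-85% |

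Without rescaling (scenarios 2 and 4 as printed at 450, correlation 0.3), 100 mg pain-free is 80% and 85%, and 50 mg MBS is 74% and 79%.

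**Step 5: placebo photophobia-free rate.** If every placebo rate shares one denominator between 60 and 120, only 81 and 108 give 7.4%, 59.3% and 51.9% together. Of these, 34.6% fits 81 (28/81) and 36.4% fits neither. But 28/77 = 36.4%, so a different denominator for that symptom would explain the SAP figure. Neither document gives denominators.

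**The case against.** The strongest reply is that nothing is hidden. The section reports the 71%, calls that scenario the most conservative, and prints the table; three of the four scenarios exceed 80%. The section describes a two-sample comparison of proportions, which is per-comparison power, and nowhere claims more than 90% for the sequence. The fixed order controls type I error whatever the power. Most of this stands. The sequence point is an unreported consequence and not an arithmetic error. Earlier disclosure does not rescue an unqualified summary sentence that contradicts the table above it.

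Several stronger readings are tempting, and the documents do not support them:

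- *The table contradicts the figures above 90%.* It has only MBS rows; all 50 mg and 100 mg entries are at least 90.1%, and the pain-free figures reproduce.
- *The figure above 95% for 50 mg is false.* It matches the only 50 mg run at 570. The phrase about all four scenarios follows the 100 mg clause, so the sentence is ambiguous.
- *Sequence power is below 90% in every scenario.* The point estimates are, but scenario 4 at 100 mg misses by about one point or less (89.1% to 89.6%) after rescaling. The assumption-free ceilings in scenarios 2 and 4 are 92.4% and 92.8%, so 90% is not strictly excluded there. The 50 mg rows for scenarios 2 and 4 are also identical in all five seeds, so they may not be separate evidence.
- *The MBS test has fewer than 570 per arm.* SAP 11.3 does exclude subjects without a baseline symptom, but the plan calls the 570 evaluable and gives no rate for this loss, so no size can be attached.
- *The SAP photophobia rate is a typing error for 34.6%.* That is plausible, but it assumes a common denominator of 81.

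**Conclusion.** The point holds in a limited form. The summary sentence is wrong for scenario 1: about 71% at 570 per arm, against a stated floor near 80%. This rests on the plan's own table and needs no assumption. The ceiling of about 71% (scenario 1) or 82% (scenario 3) on confirmatory power at 100 mg and 50 mg follows from the testing order alone, apart from a negligible rescaling from 575 to 570 in scenario 3. The step-by-step cumulative figures also rest on normal rescaling and on the assumed pain/MBS correlation of 0 to 0.5; varying that correlation moves them by about two points at most.

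A reader might infer that the trial is too small or its testing order unsound. Neither follows: the single-test powers are otherwise as stated, and type I error control is unaffected. The photophobia mismatch is real, but its effect on power cannot be calculated from the documents.

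**What to change.** In Protocol 10.1, the matching synopsis text, and SAP 2.2:

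1. Restate 200 mg MBS power by scenario: 71% to 91% as printed, about 71% to 96% at a common 570.
2. Restate 50 mg MBS power: 90.7% to 96.3% as printed (scenario means), about 90% to 98% at 570.
3. Rerun all four scenarios at 570, replacing the rescaled values above, and confirm that the identical 50 mg rows are intended.
4. Label the stated powers as per-comparison, and add the cumulative power at each step of SAP 11.1 with the pain/MBS correlation it assumes.
5. Reconcile the placebo photophobia-free rate (34.6% or 36.4%) against the Phase 2 source, and use the confirmed value in the rerun.

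The cost is text and table edits plus one rerun of an existing simulation. The only downside is that the stated figures become less favourable. Sample size, test order and alpha stay as they are.
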